| 10.3.2 | Pharmacokinetic Analyses..... | 44 |
| 10.3.2.1 | Pharmacokinetic Parameter Estimation..... | 44 |
| 10.3.2.2 | Pharmacokinetic Statistical Inference | 44 |
| 10.3.3 | Exploratory Pharmacodynamic Analyses | 44 |
| 10.3.4 | Evaluation of Immunogenicity | 44 |
| 10.3.5 | Data Review During the Study | 44 |
| 10.3.6 | Interim Analyses | 45 |
| 11 | References | 46 |

List of Tables

| Table | | Page |
|--------------|---|-------------|
| Table 4.1. | Objectives and Endpoints | 16 |
| Table 5.1. | Margin of Safety for Intravenous Administration of LY3451838 Based on Administered Dose and Predicted Exposure | 21 |

List of Figures

| Figure | | Page |
|---------------|---|-------------|
| Figure 5.1. | Illustration of study design for Protocol J1H-MC-LAJA. | 17 |

List of Appendices

| Appendix | | Page |
|-----------------|---|-------------|
| Appendix 1. | Abbreviations and Definitions | 47 |
| Appendix 2. | Clinical Laboratory Tests..... | 50 |
| Appendix 3. | Study Governance, Regulatory and Ethical Considerations..... | 52 |
| Appendix 4. | Hepatic Monitoring Tests for Treatment-Emergent Abnormality | 55 |
| Appendix 5. | Blood Sampling Summary..... | 56 |
| Appendix 6. | Protocol Amendment J1H-MC-LAJA(a) Summary..... | 57 |
| Appendix 7. | Protocol Amendment J1H-MC-LAJA(b) Summary | 60 |
| Appendix 8. | Protocol Amendment J1H-MC-LAJA(c) Summary..... | 65 |
| Appendix 9. | Protocol Amendment J1H-MC-LAJA(d) Summary | 66 |

1 Protocol Synopsis

Title of Study:

A safety, tolerability, and pharmacokinetics study of LY3451838 in healthy subjects.

Rationale:

LY3451838 is a fully human immunoglobulin G (IgG4-variant monoclonal antibody) that potently and selectively binds and neutralizes pituitary adenylate cyclase-activating polypeptide (PACAP). LY3451838 is being developed as a treatment for primary headache conditions including prevention of episodic or chronic migraine and/or cluster headache. This first-in-human study of LY3451838, J1H-MC-LAJA, will investigate the safety, tolerability, and pharmacokinetics (PK) of LY3451838 administered intravenously (IV) and subcutaneously (SC) in healthy subjects.

Objective(s)/Endpoints:

| Objectives | Endpoints |
|--|--|
| Primary | |
| Evaluate the safety and tolerability of a single dose of LY3451838 in healthy subjects | 
 • Adverse events • Serious adverse events |
| Secondary | |
| Evaluate the pharmacokinetics of LY3451838 in healthy subjects following a single dose of LY3451838. | 
 • AUC • C_{max} |

Abbreviations: AUC = area under the concentration-time curve; C_{max} = maximum drug concentration

Summary of Study Design:

Study J1H-MC-LAJA is a first-in-human, investigator- and subject-blind, placebo-controlled, randomized, 2-part study in healthy subjects to evaluate the safety, tolerability, and pharmacokinetics of LY3451838. In Part A, the single ascending doses of LY3451838 will be administered IV in up to 6 cohorts of 8 subjects each. In Part B, a single dose of LY3451838 will be administered SC in up to 2 cohorts of 8 subjects each.

Safety / tolerability, pharmacokinetic, immunogenicity, and exploratory pharmacodynamic assessments will be performed at prescribed time points during the stay at the clinical research unit (CRU) and at subsequent study visits.

All available safety and PK data will be reviewed before each dose escalation. The proposed doses may be adjusted after review of available data from previous dose levels after consultation with a Safety Review Panel (SRP) that is independent of the team.

Treatment Arms and Planned Duration for an Individual Subject:

In both parts, within each cohort, subjects will be randomly assigned to receive LY3451838 or placebo in a 6:2 ratio.

Part A: LY3451838 will be administered IV, at single ascending dose levels, starting at 25 mg and escalated up to 1500 mg.

Part B: LY3451838 will be administered SC as a single dose, which is planned as a 250 mg dose or a dose that matches that of Cohort 3 in Part A. Up to 2 cohorts in Part B may be enrolled to explore various features of SC dosing at the same dose level.

In both parts, subjects will be followed for approximately 20 weeks following administration of the study drug.

Number of Subjects:

Up to 80 healthy subjects may be enrolled so that approximately 6 subjects in each LY3451838 dosing group complete the 20-week study. Any subject who was withdrawn before completion of all study activities may be replaced at the discretion of the Sponsor.

Statistical Analysis:

Safety: The primary safety endpoints are the numbers and types of treatment-emergent serious adverse events and adverse events. Summary statistics for each cohort will be provided by dose level and for all placebo subjects combined.

Pharmacokinetics: Plasma LY3451838 PK (e.g., C_{max} , $AUC_{0-\infty}$) will be calculated using noncompartmental methods. Pharmacokinetic parameters will be summarized by dose level using descriptive statistics. Dose proportionality will be assessed. Mean and individual LY3451838 plasma concentration-time curves will be presented. Absolute bioavailability will be calculated based on data from the IV and SC cohorts.

2 Schedule of Activities

Study Schedule Protocol JAH-MC-LAJA – Part A (Intravenous Administration) and Part B (Subcutaneous Administration)

| Study Visit | 1 | 2 | 3 | 4 | 5 | 6 | 7 | 8 | 9 | 10 | 11 | 12 | 13 | 14 | 15 | 16 ^a |
|---|-----|----------------|---------------------------------------|---------------------------------------|-----------------|---|---|--------------------|------------|------------|------------|------------|------------|------------|------------|---------------------|
| Study Day | -28 | -1 | 1 | 2 | 3 | 5 | 7 | 9 (-1 to +2) | 15 (±2) | 22 (±3) | 29 (±3) | 43 (±3) | 57 (±4) | 71 (±4) | 85 (±7) | 141 / ED (±7) |
| Visit Type | S | A | I | I | D | O | O | O | O | O | O | O | O | O | O | O |
| Informed consent | X | | | | | | | | | | | | | | | |
| Medical history | X | | | | | | | | | | | | | | | |
| Height/weight ^b | X | | X | | | | | | | | X | | X | | X | X |
| Medical Assessment ^c | X | X ^d | X | X | X | X | X | X | X | X | X | X | X | X | X | X |
| Neurological examination | X | X ^d | | X | | X | | | | X | | X | | | | X |
| Electrocardiogram ^e | X | X ^d | Predose, 1, 3 h | 24 h (± 90 m) | X | X | X | X | X | X | | X | | X | | X |
| Vital signs ^{f, g} | X | X ^d | Predose, EOI ^h , 1, 3 h | 24 h (± 90 m) | X | X | X | X | X | X | X | X | X | X | X | X |
| Orthostatic BP and pulse rate | | | Predose, 1 h | 24 h | | | X | | X | | X | | | | | X |
| Pregnancy test (urine) | X | X ^d | | | | | | | | | X | | X | | | X |
| Screening tests | X | | | | | | | | | | | | | | | |
| Eligibility review | | X ^d | | | | | | | | | | | | | | |
| Study drug administration | | | X | | | | | | | | | | | | | |
| Hematology and chemistry ⁱ | | X ^d | Predose | X | X | X | X | X | X | X | X | X | X | X | X | X |
| C3, C4, CRP and ESR | X | | Predose | X | | X | | X | | X | | X | | | | |
| Urine analysis | | X ^d | | X | | X | | X | | X | | | | | | |
| PK sample ⁱ | | | EOI ^h , 3, 6, 8, 12 h | 24 h (± 60 m), 36 h (± 60 m) | 48 h (±60 m) | X | X | X | X | X | X | X | X | X | X | X |
| PACAP sample ⁱ | | | Predose, EOI ^h 6, 12 h | 24 h | 48 h | | X | | X | | X | | X | | X | X |
| Immunogenicity sample | | | Predose | | | X | | X | | X | | X | | X | | X |
| Samples for infusion and hypersensitivity reactions ^j | | | Predose | | | | | | | | | | | | | |
| Non-genetic biomarker sample | | | Predose | | | X | | | | | | | | | | |
| PGx sample ^k | | | Predose | | | | | | | | | | | | | |

| Study Visit | 1 | 2 | 3 | 4 | 5 | 6 | 7 | 8 | 9 | 10 | 11 | 12 | 13 | 14 | 15 | 16 ^a |
|-------------------------|-----|----|---|---|---|---|---|--------------------|------------|------------|------------|------------|------------|------------|------------|---------------------|
| Study Day | -28 | -1 | 1 | 2 | 3 | 5 | 7 | 9 (-1 to +2) | 15 (±2) | 22 (±3) | 29 (±3) | 43 (±3) | 57 (±4) | 71 (±4) | 85 (±7) | 141 / ED (±7) |
| Visit Type | S | A | I | I | D | O | O | O | O | O | O | O | O | O | O | O |
| Adverse events | | | | | | | | | ← X → | | | | | | | |
| Concomitant medications | | | | | | | | | ← X → | | | | | | | |

Abbreviations: A = CRU admission; BP = blood pressure; CRU = clinical research unit; D = CRU discharge; ED = early discontinuation; EOI = end of infusion; h = hour; I = inpatient stay; m = minute; O = outpatient; C3 = total complement C3; C4 = total complement C4; CRP = C reactive Protein; ESR = erythrocyte sediment rate; PACAP = pituitary adenylate cyclase-activating polypeptide; PGx = pharmacogenomics; S = screening.

Note: if multiple procedures take place at the same time point, the following order of the procedure should be used: electrocardiogram, vital signs, and venipuncture. Unless otherwise specified, predose samples may be taken at any time prior to dosing, based on CRU activity schedule.

a in case of early discontinuation/withdrawal, the subject should undergo all Visit 16 activities.

b Height will be collected at Screening only.

c Full medical assessment prior to first dose (on Day -1 or Day 1), discharge, and discontinuation visits. Symptom-driven medical assessment as deemed necessary by the Investigator.

d Day -1 samples/activities could be collected/Performed up to 5 days before the scheduled day of dosing. The medical assessment, neurological examination and eligibility review may be performed pre-dose on Day 1. If screening visit is within 1 week (inclusive) of Day -1, neurological examination, ECG, hematology and chemistry do not need to be repeated.

e Single electrocardiogram will be collected at Screening and CRU admission only. Triplicate electrocardiograms will be collected at all other timepoints.

f Vital signs include blood pressure, pulse rate, and body temperature. Single measurements at Screening and CRU admission. Supine triplicate blood pressure and pulse rate at all other timepoints.

g Body temperature to be obtained as single measurement.

h End of infusion procedures are only required for Part A of the study – to be performed within 10 minutes from infusion completion..

i Predose and 24 h (postdose) samples to be collected after at least 8 hours of fasting. PK samples on day 5 and beyond should be obtained at approximately (± 2 hr) the same time of day as the dosing time on day 1.

j Samples for infusion reactions and hypersensitivity reactions will be collected and stored for all subjects. Post treatment samples (up to 3) will only be collected in subjects who experience moderate to severe infusion reactions or hypersensitivity reactions (as defined in Section 9.4.5.2).

k If sample not collected as indicated in Study Schedule table, it may be collected a following visit.

3 Introduction

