inflammation was observed, but was attributed to immune complex deposition and, therefore, not expected to be relevant to human safety. In addition to the vasculitis, which was not evident clinically, a greater incidence of transient neurological effects was observed in treated compared to control monkeys. This included decreased or absent flexor reflexes, proprioceptive positioning, placing reactions of limbs, and locomotor stereotypy all of which were considered nonadverse. More details about the toxicology studies are provided in Section 4 of the Investigator's Brochure ([IB 2018](#)).

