3.3 Benefit/Risk Assessment

The nonclinical safety and pharmacology information for LY3451838 adequately supports the transition from preclinical status to a clinical, first-in-human study. The risk evaluation of LY3451838 through its properties, nature of the target, non-clinical data in relevant species, target population and dose projections, suggest it not be considered a high risk molecule.

LY3451838 is a novel monoclonal antibody against PACAP, a neuropeptide that is expressed in both central nervous system and peripheral tissues. While pharmacology of this mechanism has not been directly evaluated in humans, AMG301, a monoclonal antibody against PAC1 receptor, has successfully completed phase 1 clinical testing, and is being evaluated for migraine prevention in an ongoing phase 2 trial. The study of AMG301 in phase 2 suggests that blocking at least part of the PACAP pathway did not lead to significant toxicity in humans. The dose-limiting toxicity of LY3451838 was minimal-to-mild vasculitis in multiple organs in monkeys assessed after 8 weekly IV doses of 250 mg/kg, similar to the presentation of vasculitis due to immune response in toxicology species observed with other monoclonal antibodies ([Kronenberg et al. 2017](#)). Immunohistochemistry studies of tissue samples from the 8-week monkey GLP toxicology study demonstrated that the vasculitis was due to immune complex deposition and complement activation. This type of immune response in a single animal species is considered to translate poorly to human safety (EMEA). For this first in human study, the highest dose is limited to 1500 mg, which is predicted to reach an exposure approximately 15-fold lower than the concentration in which vasculitis was observed in monkeys. In addition, PK data will be reviewed with each dose escalation, and an exposure limit will be implemented in this study so that the predicted mean exposure based on observed PK does not significantly exceed that of the no-observed-adverse-effect-level (NOAEL) exposure observed in monkeys.

Immunogenicity and hypersensitivity reactions, including infusion reactions, acute and delayed (including immune complex disease) hypersensitivity reactions are a potential risk for all monoclonal antibodies, including LY3451838. Hypersensitivity risk mitigation in this study includes the administration of a single dose of LY3451838 IV with subsequent close monitoring.

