5.4 Scientific Rationale for Study Design

This study is designed to evaluate safety, tolerability, and PK of LY3451838 after single IV and SC dose administration in healthy subjects to provide the most unbiased assessment of safety and tolerability in this first-in-human study.

Hypersensitivity reactions, including both acute hypersensitivity reactions and immune complex diseases, are potential risks for all therapeutic antibodies, including LY3451838. Subjects with a history of clinically significant hypersensitivity reactions / conditions, or autoimmune diseases are excluded from the study to minimize risks for hypersensitivity reactions in the subjects in this study, and to avoid confounded interpretation of the safety data. Additional measures will be implemented to monitor and manage infusion reactions (Section 7.4.3.2), immunogenicity, and hypersensitivity reactions (Section 9.6.1). While vasculitis observed in the monkey toxicology studies was attributed to immune complex deposition, additional precautions, such as reviewing PK data before each dose escalation, limiting the dose range and implementing the exposure to that of the monkey NOAEL are designed into the protocol to address the uncertainty of the mechanism for vasculitis.

Because of the distribution of PACAP in the nervous system, and to follow-up on the subtle non-adverse changes in the neurological examination in the 2-month monkey toxicology study, neurological examinations will be performed to detect any early signals on the effects of LY3451838 on the nervous system.

Pharmacokinetic data will be used to guide dose escalation for all cohorts in Part A of the study; dose modification criteria are described in Section 7.4.1. Because the exposure after SC dosing is

[figure not shown]
expected to be less than with IV dosing for the same dose, sentinel dosing is not required in Part B of the study.

The predicted half-life of LY3451838 is 12 days, based on the allometric scaling from monkey PK data. A parallel-group design is used in both Part A and Part B of the study to avoid a prolonged washout period between doses and to avoid the potential to confound treatment-emergent antidrug antibody (TEADA) assessment. The monitoring period for this study is approximately 20 weeks after the last dose. This monitoring period duration supports adequate immunogenicity monitoring during the washout of LY3451838.

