9.4.5.2 Hypersensitivity reactions

Acute and serious hypersensitivity reactions will be assessed and managed as clinically indicated. The clinical information, including examination findings, laboratory testing and treatment for all serious adverse events, including hypersensitivity reactions, will be captured in the EDC.

Non-acute hypersensitivity reactions, including type 3 hypersensitivity reaction will be assessed by clinical presentation. Routine monitoring of vital signs with regular physical examinations, and laboratory testing (including hematology, liver and renal testing, complements C3 and C4, c-reactive protein [CRP] and erythrocyte sedimentation rate [ESR], and urine analysis) will be undertaken to assess for the development of vasculitis, serum sickness and other manifestations of type 3 hypersensitivity reactions.

Stored serum samples for possible immune safety laboratory testing (including, but not limited to: β -tryptase, total IgE, immune-complex testing, and cytokine panel) will be collected for all subjects before study drug administration (Section 2). Additional, unscheduled, stored serum samples for possible immune safety laboratory testing should also be collected approximately 60 to 120 minutes and 4 to 6 weeks after moderate or severe infusion reactions or hypersensitivity reactions.

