Appendix 5. Blood Sampling Summary

This table summarizes the approximate number of venipunctures and blood volumes for all blood sampling (screening, safety laboratories, and bioanalytical assays) during the study.

Protocol J1H-MC-LAJA Sampling Summary – Part A and B

| Purpose | Blood Volume per Sample (mL) | Number of Blood Samples | Total Volume (mL) |
|--|------------------------------|-------------------------|-------------------|
| Screening tests ^a | 21 | 1 | 21 |
| Hematology and chemistry - laboratory tests (fasting) ^a | 10 | 2 | 20 |
| Hematology and chemistry - laboratory tests (non-fasting) ^a | 8 | 13 | 104 |
| Pharmacokinetics | 2 | 19 | 38 |
| Blood discard for cannula patency | 0.3 | 8 | 2.4 |
| Pharmacodynamics (PACAP) | 10 | 12 | 120 |
| Immunogenicity | 10 | 7 | 70 |
| Pharmacogenetics | 10 | 1 | 10 |
| Non-pharmacogenetics | 10 | 2 | 20 |
| Infusion/Hypersensitivity reactions ^a | 8.5 | 1 | 8.5 |
| Total | | | 413.9 |
| Total for clinical purposes [rounded up to nearest 10 mL] | | | 420 |

^a CRP, ESR, C3 and C4 will be tested using chemistry and/or hematology samples. Additional samples, including for hypersensitivity analyses, may be drawn if needed for safety purposes.

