### 9.3 Laboratory Tests

The test results of clinical chemistry, hematology and urinalysis are to be summarized by visit. Change from baseline to each post-baseline visit will also be provided. When applicable, all the test result in the following list will be presented.

Clinical Chemistry:	Hematology:
Alkaline phosphatase	Erythrocytes count (RBC)
Alanine Aminotransferase	Hematocrit
Aspartate Transaminase	Hemoglobin
Albumin	Mean cell volume
Blood urea	Mean cell hemoglobin
Bicarbonate	Mean cell hemoglobin concentration
Total Bilirubin	Leukocyte count (WBC)
Calcium	Platelets
C-reactive Protein	Basophils
Complement 3	White blood cell count + differential
Complement 4	Erythrocyte sedimentation rate (ESR)
Sodium	
Total cholesterol	Urinalysis:
Chloride	pH
Creatinine	Specific gravity
Glucose	Blood
Potassium	Nitrite
	Bilirubin
	Ketones
	Protein
	Glucose
	Urobilinogen
	Leukocytes
	Microscopy

Additional analysis will be performed to C3, C4, CRP and ESR.

The number and percentage of subjects with significant decrease in C3 and C4 will be summarized at each of the scheduled visits by treatment and by cohort.

The number and percentage of subjects with significant increase in CRP and ESR will be summarized at each of the scheduled visits by treatment and by cohort.

The significant decrease in C3/C4 will be met if the lab result is classified as NORMAL at baseline, and classified as LOW (<LLN) at post-baseline visits, OR the lab result is classified as LOW at baseline(<LLN), and result gets LOWER than baseline at post-

baseline visits. The significant increase in CRP/ESR will be met if the lab result is classified as NORMAL at baseline, and classified as HIGH ( $>\text{ULN}$ ) at post-baseline visits, OR the lab result is classified as HIGH at baseline( $>\text{ULN}$ ), and result gets HIGHER than baseline at post-baseline visits.

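### The five tests named for type 3 reactions (C3, C4, CRP, ESR, urinalysis) have no clearly scheduled result at the last two ADA visits or at early discontinuation

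*Protocol*

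**What the plan says.** Protocol Section 9.4.5.2 says that routine vital signs, physical examination and laboratory tests "will be undertaken to assess for the development of vasculitis, serum sickness and other manifestations of type 3 hypersensitivity reactions". The tests it names are hematology, liver and renal tests, C3, C4, CRP, ESR and urine analysis.

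In the protocol schedule (Section 2), the complement/CRP/ESR row begins "C3, C4, CRP and ESR | X | | Predose | X", continues at Visits 6, 8, 10 and 12, and is then blank. The urinalysis row stops at Visit 10. The SAP reprints the schedule in Section 4.2 with both rows stopping at Visit 10. SAP Section 2 says that the SAP prevails over the protocol where they disagree.

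Visit 16 (Day 141) doubles as the exit visit for early leavers: "in case of early discontinuation/withdrawal, the subject should undergo all Visit 16 activities". Both rows are blank there.

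ADA samples continue at Visit 14 (Day 71) and Visit 16. Protocol Section 5.4 justifies the 20-week follow-up this way: "This monitoring period duration supports adequate immunogenicity monitoring during the washout of LY3451838".

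On the analysis side, SAP Section 9.3 states: "The number and percentage of subjects with significant decrease in C3 and C4 will be summarized at each of the scheduled visits". It treats increases in CRP and ESR in the same way, and Table 14.3.4.4 carries the results.

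**The concern.** Safety is the primary objective, and protocol Section 3.3 names the dose-limiting monkey finding: "minimal-to-mild vasculitis in multiple organs in monkeys assessed after 8 weekly IV doses of 250 mg/kg". It attributes this to immune-complex deposition and complement activation. Section 9.4.5.2 answers that hazard with a specific set of markers. Those markers have no clear place in the schedule after Day 43, while the search for the antibodies that could form immune complexes goes on to Day 141.

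Two things are at stake. First, a subject who first becomes TEADA+ at Day 71 or Day 141 would have no clearly scheduled complement, CRP or ESR value beside that result, and no urinalysis. Second, subjects who leave early get the Visit 16 list, so they leave without a clearly scheduled value for any of the five tests. That group includes Part A subjects whose infusion is stopped for any reason, because Section 8.1 sends them to the early-discontinuation procedures.

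**Working it through.** **1. Can the machine-read schedule be trusted?** Its rows were counted against Appendix 5 of the protocol.
- Hematology/chemistry: 15 marks (Visits 2 to 16) against 2 + 13 = 15.
- PK: 19 against 19. PACAP: 12 against 12. Immunogenicity: 7 against 7.
- Volumes: 21 + 20 + 104 + 38 + 2.4 + 120 + 70 + 10 + 20 + 8.5 = 413.9 mL, as stated.

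The counts agree. They do not prove column positions, and Appendix 5 has no separate line for the tests at issue. The superseded schedule copies in the amendment summaries also mark nothing in either row after Day 43.

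**2. Post-dose visits by row**

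| Row | Protocol Section 2 | SAP Section 4.2 |
|---|---|---|
| C3/C4/CRP/ESR | Days 2, 5, 9, 22, 43 | Days 2, 5, 9, 22 |
| Urinalysis | Days 2, 5, 9, 22 | Days 2, 5, 9, 22 |
| ADA | Days 5, 9, 22, 43, 71, 141 | Days 5, 9, 22, 43, 71, 141 |
| Hematology/chemistry | every visit to Day 141 | every visit to Day 141 |

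**3. ADA visits with a same-visit marker**
- C3/C4/CRP/ESR, protocol row: Days 5, 9, 22 and 43, so 4 of 6. Days 71 and 141 are unpaired.
- C3/C4/CRP/ESR, SAP row: 3 of 6.
- Urinalysis, either document: 3 of 6.

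**4. Follow-up after the last marked test** = (141 − last day) / 140.
- Last test Day 43: 98/140 = 70%. At the late edge of the ±3-day window (Day 46): 95/140 = 68%.
- Last test Day 22 (urinalysis in both documents; the blood tests in the SAP copy): 119/140 = 85%.

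**5. Drug remaining** = 0.5^((day − 1)/12). This uses the predicted 12-day half-life in Section 5.4 and assumes mono-exponential decline.
- Day 22: 0.5^1.75 = 30%.
- Day 43: 0.5^3.5 = 8.8%.
- Day 71: 0.5^5.83 = 1.8%.
- Day 141: 0.5^11.67 = 0.03%.

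**6. The alternative reading.** Appendix 2 lists C3, C4 and CRP under clinical chemistry and ESR under hematology. The hematology/chemistry row runs to Visit 16. Read literally, the four blood tests would be done at every visit, all 6 ADA visits would be paired, and the blood-test gap would be zero. The separate schedule row would then serve no purpose, so this is the less natural reading, but the protocol does not exclude it. Urinalysis is its own block in Appendix 2 and its own schedule row, so its gap remains on any reading.

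**The case against.** The strongest reply is that the plan is not bare after Day 43. Hematology, chemistry (so liver and renal tests), vital signs, medical assessment and AE collection run to Day 141 and are part of the exit visit. Recognized moderate or severe infusion or hypersensitivity reactions trigger stored serum at 60 to 120 minutes and at 4 to 6 weeks (Section 9.4.5.2). Hypersensitivity reactions also trigger extra ADA, drug and PACAP samples (Section 9.6.1), and Appendix 5 allows further safety samples. All of this stands. It confines the gap to five tests. It does not close it, because the stored serum is only for possible testing and depends on someone recognizing a reaction.

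Sampling is also concentrated where exposure is highest: about 91% of the drug is predicted to be gone by Day 43, and four of six post-dose ADA visits are already paired. That stands too. The 70% to 85% of days is a count of calendar time and not a measure of missed risk.

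A reader might infer from the monkey study that vasculitis appears only after about 50 days, later than the last test here. The documents do not support this. Eight weekly doses is when tissue was assessed, not when lesions began. Dosing was repeated, while this trial gives one dose at a predicted exposure about 15-fold lower (Section 3.3). The remark "In addition to the vasculitis, which was not evident clinically" is a fair reason not to rely on symptoms alone. It does not show that complement, CRP or ESR would have found the lesion.

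A reader might also infer that the report could claim 20 weeks without a complement signal. Table 14.3.4.4 is laid out by visit, so the last tested visit would be visible.

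**Conclusion.** The point holds as a limited and inexpensive improvement. By the schedule rows, C3/C4/CRP/ESR end at Day 43 in the protocol and Day 22 in the SAP, and urinalysis ends at Day 22 in both. Days 71 and 141 and every early-discontinuation visit have no clearly scheduled result for any of the five tests. The gap is clearest for early leavers.

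It would be too strong to say that the four blood tests stop by Day 43 on every reading, because Appendix 2 permits another. For those four, the finding is an unresolved contradiction between the schedule row, the SAP copy and Appendix 2. For urinalysis it is a plain absence. It would also be too strong to say that immune safety monitoring stops, or that the protocol breaks a promise: Section 5.4 ties the 20 weeks to immunogenicity monitoring and does not commit to these markers throughout.

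The conclusion rests on the column positions of machine-read tables. The drug-remaining figures also rest on the predicted half-life and mono-exponential decline, but the finding does not depend on them.

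**What to change.** - Reconcile the protocol schedule row, the SAP schedule row and Appendix 2, and state which governs C3, C4, CRP and ESR.
- Run these four assays at Visit 14 and Visit 16/early discontinuation. No new venipuncture is needed: Appendix 5 says "CRP, ESR, C3 and C4 will be tested using chemistry and/or hematology samples", and those samples are already drawn at both visits.
- Add a urine dipstick at Visit 16/early discontinuation.
- Extend SAP Table 14.3.4.4 to the added visits, and list C3, C4, CRP and ESR by visit for TEADA+ subjects. The urinalysis table (14.3.4.3) is by visit and would take the added dipstick.

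The cost is a few schedule marks, some extra assays on existing tubes and one short listing. The downside is a few more incidental out-of-range CRP or ESR values in healthy subjects to explain.

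SAP Section 6 already refers to locked data, so visits may be complete. In that case, the report should state that the schedule rows carried complement, CRP and ESR only to Day 43 and urinalysis only to Day 22, and should say whether the blood tests were in fact run later as part of the chemistry and hematology panels.
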